1.5 Secondary Analysis

- 1.5.1 Linear regression models will be used to estimate the between group difference in 24-hour change in each of the secondary outcomes; 95% confidence intervals will be constructed using t-based methods.

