Study Product, Dose, Route, Regimen	Patients will be randomized 1:1 to ultra-high dose (IV bumetanide 12.5 mg bid) vs standard dose (IV furosemide as twice the home dose of oral daily diuretic in furosemide equivalents administered bid) for 24 hours. Participants will undergo comprehensive physiological assessment at baseline and 24 hours with short Iohexol clearance for true glomerular filtration rate, apnea hypopnea index, electrocardiography, echocardiography, serum, and urine biomarkers. Patients will be monitored for side effects including muscle cramps, new onset atrial fibrillation (AF), sustained ventricular tachycardia (VT), symptomatic hypotension (MAP<60 or systolic blood pressure <80 mmHg), development of renal insufficiency and dialysis initiation.
Duration of Administration	Patients will be on therapy for 24 hours.

Statistical Methodology	The primary efficacy endpoint is urine output over 24 hours which will be compared by T test between the two groups. Primary safety endpoint will be incident decline in creatinine estimated glomerular filtration rate by 50% over 24 hours. Key secondary endpoints include weight change, NT-proBNP change, urine output, urine sodium excretion, creatinine, and cystatin C estimated GFR changes, apnea-hypopnea index, Iohexol glomerular filtration rate, serum and urine proteomic analyses, peripheral vein pressure and echocardiographic changes over 24 hours, estimated GFR at day 7 or discharge (whichever is sooner) will each be compared by T test between the two groups.
-------------------------	---

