In this pilot study we will therefore compare an ultra-high diuretic strategy with a conventional diuretic strategy in patients with decompensated heart failure with a primary efficacy end point of urine output at 24 hours. The primary safety endpoint will be a decline in serum creatinine estimated GFR by 50% of baseline value at 24 hours. This will be a double-blinded randomized pilot trial of ultra-high dose diuretics (IV bumetanide 12.5 mg bid for 24 hours vs IV furosemide at usual doses (twice the home dose of oral daily diuretic in furosemide equivalents administered bid). New initiation of adjunct diuretics (thiazide, SGLT2 inhibitors, acetazolamide, and spironolactone) will be discouraged during the 24-hour study period. Key secondary endpoints include weight change, NT-proBNP change, urine output, urine sodium excretion, creatinine, and cystatin C estimated GFR changes, apnea-hypopnea index, iohexol glomerular filtration rate, serum and urine proteomic analyses, peripheral vein pressure and echocardiographic changes over 24 hours, estimated GFR at day 7 or discharge (whichever is sooner) will each be compared by T test between the two groups.

4.2 Hypothesis:

Ultrahigh dose diuretic infusion will be associated with greater diuretic response and will not be associated with clinically significant decline in eGFR over 24 hours (defined as decline in creatinine estimated GFR of 50% from baseline at 24 hours).

4.3 Innovation:

1. Ultra-high dose diuretic strategies have not been compared to conventional diuretic strategies in a randomized trial
2. The use of a double-blind strategy will minimize bias in terms of diuretic adjustment and alternative therapies.
3. The measurement of serum and urine biomarkers of renal injury, peripheral vein pressure and echocardiography changes at baseline and at 24 hours will provide novel insight into the hemodynamic, renal, and cardiac response to decongestion.

4. The relationship between creatinine based GFR during non-steady state conditions such as active diuresis and extracellular volume reduction during diuresis, and true GFR measured by lohexol clearance testing has never been studied.
5. The effect of rapid diuresis on cardiac structure and function has not been well studied
6. The short-term effect of rapid volume removal on measures of sleep is unknown

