8.1.2 Enrollment, Baseline, and/or Randomization

After confirming eligibility, informed consent will be obtained. Following consent, patients will be randomized 1:1 to ultrahigh vs standard dose diuretic strategies.

Day 1 (0-24 hours)

After randomization, patients will undergo comprehensive baseline assessment including weight, echocardiogram, history, and physical examination. Initial randomized therapy will be administered at least 6 hours after last clinically administered dose of IV diuretic (or immediately if no IV diuretic has been administered in the last 6 hours). Participants will be urged to void their bladders and discard urine at baseline immediately prior to receiving study drug. All baseline testing will be performed when feasible once consent is obtained. Baseline testing will include blood sample testing for NT proBNP, creatinine, cystatin C and hematocrit. Urine collection for urine creatinine and sodium will be specifically collected timed 1-2 hours after the administration of study diuretic dose to allow estimation of urine sodium excretion. 32 ml of blood and 30 ml of urine will be stored for future analyses. Peripheral venous pressure will be recorded from existing IV lines through pressure transducer monitoring from study team.

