In addition to blood testing as above, Iohexol based GFR calculation using subcutaneously injected-Iohexol and timed samples of blood and urine to calculate GFR will be used for research with a procedure following typical inpatient practice Iohexol based GFR measurement. We will use the short Iohexol protocol with subcutaneous iothalamate injection (Time 0:T0), urine sampling at 1 hour after subcutaneous injection, with total urine volume collected over the 1-hour period (T0 to 1 hour). Urine and serum samples will be collected again approximately 45 minutes later from T60. Serum and urine samples for Iohexol will be collected at two time points after T0: i) T60 and ii) 45 minutes after T60. We will also continuously collect urine from subcutaneous injection until the end of the test, for quality control as per standard clinical practice. If Foley catheter is not present at baseline, participants will be asked to void voluntarily prior to renal study initiation with bladder scanning to confirm residual urine following bladder emptying. Ambulatory blood pressure monitoring (ABPM) will be recorded via an upper arm cuff on the non-dominant arm. Over a 48-hour period (Days 1 & 2), a blood pressure reading will be taken every 30 minutes during the day and every hour at night. Arterial stiffness will be assessed via carotid tonometry and placing a femoral and brachial blood pressure cuff on the upper thigh and upper arm. A liver ultrasound scan (Fibroscan) of the abdominal region will quantify liver elastography and potential liver disease.

Nocturnal screening for apnea-hypopnea index as a measure of sleep apnea will be performed using Watch Pat or Nox device. The Watch Pat is a non-invasive wrist monitor and will be worn overnight to test for sleep apnea. The Nox device is a portable polysomnography device to

measure sleep quality and determine sleep apnea presence. If patients have known sleep apnea, they will continue their home CPAP/BiPAP during the overnight test.

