1.3 Primary and Secondary Outcomes

- 1.3.1 Primary outcome: urine output at 24 hours after initiation of intravenous diuretic.
- 1.3.2 Secondary outcomes: changes in the following measures over 24 hours after initiation of intravenous diuretic:
 - 1.3.2.1 Body weight
 - 1.3.2.2 NT-proBNP change
 - 1.3.2.3 Urine sodium excretion
 - 1.3.2.4 Apnea-hypopnea index
 - 1.3.2.5 Iohexol glomerular filtration rate
 - 1.3.2.6 Peripheral vein pressure
 - 1.3.2.7 Echocardiographic measures of cardiac output, estimated RV systolic pressure, RA pressure, LA strain, LV and RV global longitudinal strain, E/e'

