1.6 Exploratory Analysis

- 1.6.1 We will quantify any differential treatment response by heart failure subtype (HFPEF, HFrEF) by including heart failure subtype as a covariate and as an interaction with the group effects in the models mentioned above.

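### Section 11.5.1, item 1.5.1 names no baseline covariate for the secondary 24-hour changes; adding the Day 1 value is a cheap gain in precision on average, unless correlation is high or Day 2 spread is larger

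*Combined protocol and SAP*

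**What the plan says.** Item 1.3.2 defines the outcomes as "Secondary outcomes: changes in the following measures over 24 hours after initiation of intravenous diuretic": weight, NT-proBNP, urine sodium excretion, apnea-hypopnea index, iohexol GFR, peripheral vein pressure and several echocardiographic measures. Item 1.5.1 gives the model: "Linear regression models will be used to estimate the between group difference in 24-hour change in each of the secondary outcomes", with t-based 95% intervals. No covariate is named and none is ruled out.

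For overlapping lists of endpoints, the Statistical Methodology row of the Study Summary says they "will each be compared by T test between the two groups", and Section 4.1 ends the same way: "estimated GFR at day 7 or discharge (whichever is sooner) will each be compared by T test between the two groups". The only covariate named anywhere in the analysis plan is heart failure subtype, in the exploratory item 1.6.1, which works "by including heart failure subtype as a covariate and as an interaction with the group effects in the models mentioned above".

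On Day 1 timing, Section 8.1.2 has urine sodium "specifically collected timed 1-2 hours after the administration of study diuretic dose". The apnea monitor "will be worn overnight to test for sleep apnea", with no stated link to the first dose. For the rest, "All baseline testing will be performed when feasible once consent is obtained".

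**The concern.** A regression with treatment group as its only term is the same as the equal-variance t test, so the three places agree on an unadjusted change score. That analysis uses the Day 1 value only by subtracting it, which fixes its coefficient at 1. If Day 1 predicts Day 2 only moderately, full subtraction adds noise that a fitted coefficient would avoid.

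Section 11.2 says the pilot is to guide a pivotal trial. With 20 patients, its secondary results will be read mainly through their confidence intervals. Unnecessarily wide intervals are a small but avoidable loss. Leaving the covariate unstated also leaves room to choose between adjusted and unadjusted results after seeing them.

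**Working it through.** **Sample size.** The plan gives no precision figure for secondary outcomes. Item 1.7.1 supplies the sizes: 10 per group, with up to 10% dropout, hence 9. Its own statement (80% power for 1688 mL, SD 1200 mL, two-sided 0.05) reproduces at 9 per group: 79.99% from the noncentral t with 16 df. That statement concerns urine output only and is not affected here.

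**Formula.** Let the baseline SD be 1, the Day 2 SD be k, the Day 1 to Day 2 correlation be ρ, and the total be N.

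- Change-score variance: 1 + k² − 2kρ.
- Residual variance after adjustment: k²(1 − ρ²), which equals the change-score variance minus (1 − kρ)². It is never larger.
- Price of estimating one more coefficient, on squared width: f = (N−3)/(N−4) × (t(N−3)/t(N−2))².
  - 10 per arm: 17/16 × (2.1098/2.1009)² = 1.0715.
  - 9 per arm: 15/14 × (2.1314/2.1199)² = 1.0831.
- Width ratio, adjusted over change score ≈ √[f × k²(1−ρ²)/(1+k²−2kρ)]. With k = 1 this is √[f(1+ρ)/2].

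**Equal SDs (k = 1).** ρ is assumed. Simulation used 100,000 normal-data trials per setting.

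| ρ | Formula, 10/arm | Simulated mean ratio, 10/arm | Adjusted narrower, 10/arm | Simulated mean ratio, 9/arm | Adjusted narrower, 9/arm |
|---|---|---|---|---|---|
| 0.3 | 0.835 | 0.83 | 90% | 0.84 | 87% |
| 0.5 | 0.896 | 0.89 | 80% | 0.90 | 76% |
| 0.7 | 0.954 | 0.95 | 63% | 0.96 | 59% |
| 0.8 | 0.982 | 0.98 | 51% | 0.99 | 48% |
| 0.9 | 1.009 | 1.01 | 36% | 1.01 | 34% |

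Break-even is ρ = 2/f − 1, which is 0.87 at 10 per arm and 0.85 at 9. Type I error was 4.8–5.2% for both models.

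**Unequal SDs.** At k = 1.2 and ρ = 0.7, the change-score variance is 1 + 1.44 − 1.68 = 0.76 and the adjusted variance is 1.44 × 0.51 = 0.734. The ratio is √(1.0715 × 0.734/0.76) = 1.02, so the gain is gone. At k = 0.8 and 10 per arm, the ratio is 0.73–0.83 for ρ from 0.3 to 0.9.

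**Largest loss.** Since the variance ratio cannot exceed 1, the average loss is capped near √f: 1.035 at 10 per arm and 1.041 at 9. A single trial can do worse. At ρ = 0.9, k = 1 and 10 per arm, one trial in ten is at least 8% wider and one in twenty at least 12%.

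**Body weight.** Section 10 reports SDs of weight change of 8.7 and 8.6 kg in retrospective 72-hour intensive-care data. With equal SDs, ρ = 1 − SDchange²/(2 SD²). An assumed baseline SD of 20 kg gives 1 − 75.7/800 = 0.905, and 30 kg gives 1 − 75.7/1800 = 0.96. Both lie above break-even, so adjustment would make weight about 1–3% wider. At 15 kg, ρ is 0.83 and there is no material difference. These data are indicative only.

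**Post-dose Day 1 values.** If treatment has already shifted the Day 1 value by d between arms, subtraction moves the estimate by −d. Adjustment moves it by −kρ·d, which is smaller whenever kρ is between 0 and 1. Adjustment is then no worse than the plan on this count.

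**Dropping patients with post-dose values.** If 2 of 10 per arm were lost, the adjusted interval at 8 per arm over the planned interval at 10 per arm would be 0.96, 1.03, 1.09, 1.13 and 1.16 at ρ = 0.3, 0.5, 0.7, 0.8 and 0.9. The exclusion would cancel the gain above ρ of about 0.4.

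**The case against.** The planned analysis is legitimate. Under randomization the change score is unbiased, and its interval already allows for chance baseline imbalance. No power claim or decision rule rests on these outcomes, and item 1.5.1 does not forbid a covariate. Choosing a change score in a 20-patient pilot is defensible. All of this stands, and it is why the point is an improvement and not a fault.

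The gain also cannot be shown from the documents. They give no correlation or baseline SD for any outcome proposed for adjustment, and weight, the one listed secondary outcome with usable change data, probably gains nothing. The creatinine change figures in Section 10 cannot fill the gap. Creatinine is not listed in item 1.3.2. Read as SDs with 29 and 73 patients (28% of 102), the values give p = 0.96 against the reported 0.81. What remains is an uneven trade: an average gain of about 5–17% at correlations of 0.7 down to 0.3 with equal SDs, against an average loss of at most about 4%.

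A reader might infer more than the documents support:

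- **That the T test wording conflicts with the regression wording.** With treatment group alone in the model, they are the same analysis.
- **That adjustment always helps, or helps only at low to moderate correlation.** With equal SDs the mean gain runs to about 0.85–0.87, and with unequal SDs correlation alone does not settle it.
- **That patients with a post-dose Day 1 value must be excluded.** The plan excludes none, and doing so can cost more precision than adjustment gains.

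**Conclusion.** This is a cheap improvement, not an error. The likely secondary analysis is an unadjusted change score, which is valid but on average less precise than baseline-adjusted regression unless ρ is high or the Day 2 SD exceeds the baseline SD. At 10 per arm with equal SDs, the mean width falls by about 17%, 11%, 5% and 2% at ρ of 0.3, 0.5, 0.7 and 0.8, and rises by about 1% at 0.9.

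The result rests on assumed correlations and SD ratios and on normal data, so skewed outcomes such as NT-proBNP may behave differently. The documents do not support a claim of bias, of invalid secondary results, or of any effect on the primary power statement. Whether change from a post-dose value is the right measure for urine sodium is a separate question that this point does not settle.

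**What to change.** Amend item 1.5.1 to add:

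> For NT-proBNP, iohexol GFR, peripheral vein pressure and echocardiographic measures, the 24-hour change will be regressed on treatment group and the Day 1 value of that measure.

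- **Leave unadjusted:** body weight, because no gain is expected; urine sodium, because its Day 1 sample follows study drug; and apnea-hypopnea index, because its first recording may do so. A Day 1 value that is post-dose by design is not a baseline covariate. Their definition as changes in item 1.3.2 stays as it is.
- **Timing:** record the time of each Day 1 test relative to the first study dose. Keep every patient in the main model even when an individual Day 1 value turns out to be post-dose, and report a sensitivity analysis restricted to pre-dose baselines.
- **Consistency:** align the T test wording in the Study Summary and Section 4.1 for the four adjusted outcome groups only. Those lists also cover creatinine and cystatin C estimated GFR, proteomics and day 7 GFR, which this change does not touch.
- **When:** date the amendment before outcomes are examined by arm, since item 1.9.1 leaves the study statistician unblinded.

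**Cost:** SAP wording, one time stamp per Day 1 test, and one residual degree of freedom per model. The exploratory subtype models inherit the covariate and go from 20 − 4 = 16 to 20 − 5 = 15 residual df. Intervals would be up to about 4% wider on average if the correlation is high or the Day 2 SD is larger.

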1.7 Sample Size Determination

- 1.7.1 Sample size was determined based on a combination of feasibility and also the variability of 24-h net urine output observed in the ATHENA-HF trial (Butler et al. 2017). Butler et al. observed a median (25th percentile, 75th percentile) net urine output of 1183 ml (510, 1955) in the usual care alone group and 1100 ml (483, 2131) in the high dose spironolactone group. **With a total sample size of 20 patients (10 per group), we will have 80% power at the alpha=0.05 level of significance (two-sided) to detect a 1688 ml difference in 24-h urine output assuming a common standard deviation of 1200 ml and a dropout rate of 10% or less.** With all other assumptions being the same, the following gives estimates of power for a range of differences. Power was estimated using nQuery Advisor version 7.0 (two group t-test of equal means).

Difference (mL)	Power
1500	70%
1600	75%
1700	80%
1800	84%
1900	88%
2000	91%

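### No transformation or baseline adjustment is specified for NT-proBNP change; if the marker is right-skewed and changes in proportion to its baseline, a few patients could weigh heavily and power could fall substantially

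*Combined protocol and SAP*

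**What the plan says.** SAP item 1.5.1 (within Section 11.5.1) gives one method for all secondary outcomes: "Linear regression models will be used to estimate the between group difference in 24-hour change in each of the secondary outcomes", and "95% confidence intervals will be constructed using t-based methods". Item 1.3.2.2 lists "NT-proBNP change" among those outcomes. The Statistical Methodology row of the Study Summary agrees. It begins "Key secondary endpoints include weight change, NT-proBNP change, urine output, urine sodium excretion" and ends by saying that the endpoints "will each be compared by T test between the two groups". Section 4.1 repeats this.

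No log or other transformation, rank-based method or check for skewness appears anywhere. The only covariate named is in the exploratory analysis (item 1.6.1), which works by "including heart failure subtype as a covariate and as an interaction with the group effects in the models mentioned above". Baseline NT-proBNP is in no model.

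The eligibility criteria (Sections 6.1 and 6.2) set no NT-proBNP range, and the Study Summary admits any ejection fraction. The only power statement (item 1.7.1) concerns urine output. No distribution, expected effect or power is given for NT-proBNP.

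**The concern.** A t-based comparison of mean change works well when the size of the change is unrelated to the starting level. If a marker instead falls by a roughly constant fraction, a patient who starts ten times higher shows a change ten times larger. The change scores then inherit the spread and skewness of the baseline. With about 10 patients per arm, the few with the highest baselines can carry much of the mean difference and of its standard error, and a real proportional effect becomes harder to see.

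Section 11.2 presents the trial as a pilot meant to inform a definitive trial. What is at stake is therefore less a p-value than a usable effect estimate and variance for this marker. A second, smaller issue is that a plan silent on scale leaves the scale open to choice after the data are seen.

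**Working it through.** **The plan's own figure.** Item 1.7.1 states that "we will have 80% power at the alpha=0.05 level of significance (two-sided) to detect a 1688 ml difference in 24-h urine output", with SD 1200 ml and up to 10% dropout, so 9 per group. Exact two-sample t-test power (noncentral t, 16 df) gives 80% at 1688 ml. At 1500, 1600, 1700, 1800, 1900 and 2000 ml it gives 70.2, 75.7, 80.5, 84.8, 88.3 and 91.3%, in line with the plan's table. That calculation is sound, but it says nothing about NT-proBNP.

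**Assumptions for NT-proBNP (none is in the documents).**
- Baseline B is log-normal with log-SD s from 0.3 to 1.2. The ratio of 75th to 25th percentile is exp(1.349 s): 1.5 at s = 0.3, 2.2 at 0.6 and 3.9 at 1.0.
- The ratio R of 24-hour to baseline value is log-normal with median g = 0.65 in one arm and 0.85 in the other, and within-patient log-SD w = 0.25 to 0.35.
- R is independent of B, so the effect is purely proportional. There are 10 patients per arm and two-sided alpha is 0.05.

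**Log scale.** The effect is ln(0.85/0.65) = 0.268.
- w = 0.25: standardised effect 0.268/0.25 = 1.07; noncentrality 1.07 × √5 = 2.40; power 62%.
- w = 0.35: standardised effect 0.268/0.35 = 0.77; noncentrality 1.71; power 37%.

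The baseline spread does not enter.

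**Raw scale.** The change is D = B(R − 1). With median B set to 1 (it cancels):
- mean(D) = exp(s²/2) × [g exp(w²/2) − 1]
- var(D) = exp(2s²) × [g² exp(2w²) − 2g exp(w²/2) + 1] − mean(D)²

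For s = 1.0 and w = 0.25:
- g = 0.65: mean −0.543, variance 0.721
- g = 0.85: mean −0.203, variance 0.437
- standardised effect = 0.340 / √[(0.721 + 0.437)/2] = 0.340/0.761 = 0.45, against 1.07 on the log scale

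The change scores are skewed, so power was obtained by simulation (20,000 or more trials per setting). Ranges are over w = 0.35 to 0.25.

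| Baseline log-SD | Power, raw change | Power, log change |
|---|---|---|
| 0.6 | 24–36% | 37–62% |
| 0.8 | 18–28% | 37–63% |
| 1.0 | 14–20% | 36–62% |
| 1.2 | 11–15% | 37–62% |

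At s = 0.3 the raw analysis keeps 84–86% of the log-scale power; at 0.6 it keeps about 60%, and at 0.8 about half.

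**Weight of individual patients.** For s from 0.6 to 1.2, the two patients with the largest changes carry a median 29–44% of the total absolute change among 20. Equal weights would give 10%.

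**No effect.** The raw-change test rejects in about 3–5% of trials, so it is slightly conservative.

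**A second set-up.** With 9 per group, a 20% mean fall in the standard arm, SD of log change 0.2 to 0.5, and the effect set to give 80% power on log change, raw-change power is:
- s = 0.3: 63–66%
- s = 0.7: 31–42%
- s = 1.0: 18–28%

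With no mean fall in the standard arm (SD of log change 0.3), it is 73% at s = 0.3 and 40% at s = 1.0. Adding baseline as a covariate on the raw scale recovers part of the loss (45–48% at s = 1.0). The log model with log baseline as covariate has about 76–78%, against 80% for log change. That gap is the price of the covariate in a set-up where log change was drawn independently of baseline, so the covariate could bring no gain.

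**The case against.** The strongest objection is that every NT-proBNP input is assumed. The documents do not say that the marker is skewed or that it changes in proportion to baseline. A simulation with log-normal baselines and a multiplicative effect is bound to favour the log scale. If change were additive and unrelated to baseline, the raw scale would cost nothing. This stands, and it is why the size can be given only as a conditional range.

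A reader might infer that a few patients dominate the estimate and that most of the power is lost. The documents do not support that as a fact. Even under the assumptions above, two of 20 patients carry less than half of the absolute change, and most of the power is lost only from a baseline log-SD of about 0.8 to 1.0 upward. A reader might also infer that the plan chose the raw scale. It is silent: raw change is the natural reading of the model, but no wording says untransformed.

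The consequence is also limited. NT-proBNP is one of several secondary outcomes reported with unadjusted p-values (item 1.10.1) in a 20-patient pilot, with no power claimed for it. Body weight, peripheral vein pressure, RA pressure and E/e' also bear on congestion. At 37–62% power on the log scale, the marker stays underpowered after the change.

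These points limit the size of the loss. They do not remove the gap in specification, and they do not argue against closing it at the cost of one sentence.

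**Conclusion.** The point holds as a gap in specification with a conditional cost. The plan names neither a scale nor a baseline adjustment for NT-proBNP. If the marker is right-skewed and changes roughly in proportion to baseline, high-baseline patients could weigh heavily on the mean difference and its interval, and power could fall substantially: from 37–62% to 24–36% at a baseline log-SD of 0.6, and from 36–62% to 14–20% at 1.0. These figures assume 24-hour ratios of 0.65 versus 0.85, 10 patients per arm and a within-patient log-SD of 0.25 to 0.35. The loss is small at a log-SD of 0.3 and vanishes if change does not depend on baseline.

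A reader might also fear false-positive findings or damage to the main result. Neither follows: type I error is not inflated, and the analysis of 24-hour urine output does not use this marker.

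**What to change.** In items 1.3.2.2 and 1.5.1, state that NT-proBNP will be analysed as log NT-proBNP at 24 hours in the same linear model, with log baseline NT-proBNP as a covariate, and reported as the between-arm ratio of geometric means with its t-based 95% CI. At minimum, analyse the log of the ratio of the 24-hour to the baseline value; this remains a t test, as the Study Summary and Section 4.1 describe. If the covariate is used, those two places should refer to the SAP model for this outcome.

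The cost is one sentence. Both measurements are already in the Schedule of Events, so no new data, visits or patients are needed. The result is read as a percentage difference instead of pg/mL, and the covariate uses one degree of freedom (residual df 17 instead of 18 with 20 patients).
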